
Study Coordinator [name], CRCA Division of blood and Marrow Transplantation Stanford University Medical Center [name]
	
Study Coordinator [name], CRCA Division of blood and Marrow Transplantation Stanford University Medical Center [name]

Biostatistician [name] Department of Health Research and Policy Biostatistics Shared Resource, [name]
	

TABLE OF CONTENTS

Protocol Synopsis	4
List of Abbreviations and Definition of Terms	5
Schema	6
1. Objectives	7
1.1 Primary Objective	7
1.2 Secondary Objectives	7
2. Background and Rationale	7
3. Participant Selection and Pre-Enrollment Requirements	10
3.1 Patient Inclusion Criteria (on Participant Eligibility Checklist)	11
3.2 Patient Exclusion Criteria (on Participant Eligibility Checklist)	12
3.3 Informed Consent Process	14
3.4 Study Timeline	14
4. Treatment Plan	15
4.1 Treatment Schedule	15
4.2 Criteria for Removal	15
4.3 Alternatives	16
4.4 Compensation	16
5. Adverse Events and Reporting Procedures	16
5.1 Adverse Events	16
5.2 Adverse Event Reporting	17
6. Data Capture	17
7. Study Calendar	19
8. Measurements and Statistical Methods	21
9. Regulatory Considerations	21
10. Statistical Considerations	22
10.1 Statistical Analysis	22
10.2 Stopping Rule	22
10.3 Sample Size	23
10.4 Accrual Estimate	23
References	24
Appendix A Glucksberg clinical stage and grade of acute GVHD	26
Appendix B Response Criteria by Disease Histology	27

Protocol Synopsis

[figure not shown]
TITLE	Very Low-dose Total Body Irradiation in Combination with Total Lymphoid Irradiation and anti-Thymocyte Globulin to Improve Donor Engraftment in Patients Undergoing Non-Myeloablative Hematopoietic Cell Transplantation for Leukemia and Lymphoma
STUDY PHASE	Phase 2

STUDY SITE	Stanford University Medical Center, CA 94305
INDICATION	Patients with leukemia and lymphoma who are not eligible for myeloablative transplantation
STUDY AGENT	The addition of low-dose total body irradiation to total lymphoid irradiation and anti-thymocyte globulin as transplant conditioning therapy
PRIMARY ENDPOINT and OBJECTIVE(S)	To determine the proportion of patients with full donor T-cell chimerism at Day 28 following hematopoietic cell transplantation
SECONDARY ENDPOINTS AND OBJECTIVE(S)	
 1. To determine the risk of disease progression, overall and event-free survival, and non-relapse mortality, following treatment with TLI/ATG/TBI 2. To determine the incidence of acute and chronic GVHD following treatment with TLI/ATG/TBI
STUDY OBSERVATION PERIOD	Patients will be followed for 1 year from the time of transplant
TREATMENT SUMMARY	The efficacy of non-myeloablative allogeneic transplantation is mediated in part by the establishment of an alloreactive donor T-cell compartment following transplant with minimal toxicity. The objective of this study is to evaluate whether a single administration of low-dose TBI to standard TLI/ATG non-myeloablative transplant conditioning will help to augment donor chimerism without reducing tolerability of this regimen or increasing the risk of GVHD. This is a single institution, open-label, single treatment study evaluating the efficacy of low-dose TBI added to TLI/ATG in adults with leukemia and lymphoma undergoing allogeneic HCT from sibling or unrelated donors.
SAMPLE SIZE	20 patients
SUMMARY OF SUBJECT ELIGIBILITY	
Patients with the following histologically-confirmed disease:
 
 1. Acute myeloid leukemia (AML) 2. Chronic lymphocytic leukemia (CLL) 3. Myelodysplastic syndrome (MDS) / Myeloproliferative disease syndrome (MPD) 4. Non-Hodgkin lymphoma (NHL) 5. Hodgkin lymphoma (HL) 
Patients not undergoing ablative transplant conditioning
 
Patients with HLA-matched or single antigen/allele mismatched related or unrelated donors.

CONTROL GROUP	Not applicable. Single-arm study.

LIST OF ABBREVIATIONS and DEFINITION OF TERMS

AE	Adverse event	Kg	Kilograms
AML	Acute myeloid leukemia	KPS	Karnofsky performance status
ALT	Aspartate aminotransferase	LVEF	Left ventricular ejection fraction
AST	Alanine aminotransferase	MC	Mixed chimerism
ATG	Anti-thymocyte globulin	MDS	Myelodysplastic syndrome
BID	bis in die (twice-a-day)	MEP	Megakaryocyte erythroid progenitors
CFR	Code of Federal Regulations	MG	Milligrams
cGY	Centigray	MkP	Megakaryocyte progenitors
CLL	Chronic lymphocytic leukemia	MMF	Mycophenolate mofetil
CLP	Common lymphoid progenitors	MPD	Myeloproliferative disease syndrome
CML	Chronic myelogenous leukemia	MPPS	Multipotent progenitors
CMML	Chronic myelomonocytic leukemia	NCI	National Cancer Institute
CMP	Common myeloid progenitors	NHL	Non-Hodgkin lymphoma
CNS	Central nervous system	NK	Natural killer cells
CR	Complete remission / response	NRM	Non-relapse mortality
CRF	Case report / record form	OnCore	OnCore enterprise research system
CRI	CR + incomplete blood count recovery	OS	Overall survival
CTCAE	Common Terminology Criteria for Adverse Events	PAMPS	pathogen-associated molecular pattern
DAMP	Damage-associated molecular pattern	PBSC	Peripheral blood stem cells
DLCO	Diffusing capacity – lung for carbon monoxide	PB	Peripheral blood
DLI	Donor leukocyte infusion	PCR	polymerase chain reaction
DSMC	Data Safety Monitoring Committee	PD	Progressive disease, tumor progression
EFS	Event-free survival	PR	Partial response
EP	Electrophysiology	RIC	Reduced intensity conditioning
FACS	Fluorescence activated cell sorting	SAE	Serious adverse event
FDA	Food and Drug Administration	SCI	Stanford Cancer Institute
FDC	Full donor chimerism	SD	Stable Disease
FISH	Fluorescence in situ hybridization	SGOT	Serum glutamic oxaloacetic transaminase
GCP	Good Clinical Practice	SIN	Subject identification number
G-CSF	Filgrastim, granulocyte-colony stimulating factor	SRC	Scientific Review Committee
GVHD	graft-versus-host disease	STRs	Short tandem repeats
GVT	graft-versus-tumor	TAC	Tacrolimus
GMP	granulocyte macrophage progenitors	TBI	Total body irradiation
HCT	Hematopoietic cell transplant	TBili	Total bilirubin
HL	Hodgkin lymphoma	TCD	T-cell depleted
HLA	Human leukocyte antigen	TLI	Total lymphoid irradiation
HSC	Hematopoietic stem cell	ULN	Upper limit of normal
ICH	Int'l Conference on Harmonization	URD	Unrelated donor
IRB	Institutional Review Board		

SCHEMA

1 TLI: Total lymphoid irradiation

2 TBI: Total body irradiation

3 ATG: Anti-thymocyte globulin

4 Tac: Tacrolimus (can be IV)

See also Section 8 Study Calendar

5 PBSC: Peripheral blood stem cells. The PBSC infusion procedure is called a hematopoietic cell transplant (HCT)

6 MMF: Mycophenolate mofetil. 15 mg/k PO BID for PBSC from matched-related donors; 15 mg/kg PO q8 hours for PBSC from unrelated donors (URDs) or mismatched related donors.

7 STRs: Short tandem repeats for engraftment analysis

1. OBJECTIVES

1.1 Primary Objective

1. To determine the proportion of patients with full donor T-cell chimerism at Day 28 following hematopoietic cell transplantation

1.2 Secondary Objectives

2. To determine the risk of disease progression, overall and event free survival, and non-relapse mortality, following treatment with TLI/ATG/TBI
3. To determine the incidence of acute and chronic GVHD following treatment with TLI/ATG/TBI

2. BACKGROUND

2.1 Allogeneic Hematopoietic Cell Transplantation

Allogeneic hematopoietic cell transplantation (HCT) is proven effective therapy for patients with a variety of hematolymphoid malignancies. Following allogeneic HCT, a significant percentage of patients who were otherwise considered to have incurable cancers using best of care non-transplantation therapies have long-term disease free control and appear cured. These patients are characterized by developing donor type hematopoiesis and have complete resolution of all disease-related signs, symptoms and markers. Generally, patients who undergo allogeneic HCT are doing so as a “last ditch” effort for long-term disease control and possibly cure after exhausting all chemotherapy, and radiation therapy based treatment strategies. Often many of the patients who undergo allogeneic HCT for treatment of their lymphoma have had disease relapse even after high dose chemotherapy and autologous stem cell rescue (autologous HCT).

2.2 Relapse of Disease following Allogeneic HCT

The main cause for treatment failure following allogeneic HCT is disease relapse. Depending, in part, on the disease, disease status at the time of transplantation, and the intensity of the transplantation regimen, disease relapse occurs in roughly 25 to 80% of patients. For example, following a full dose transplant in younger patients with acute leukemia in 1st or 2nd complete remission (CR) and using a graft from a HLA-matched sibling, the 2-year risk of disease relapse was < 30% [1-8]. In contrast, the 2-year risk of disease relapse for younger patients with refractory acute leukemia who received a full-dose transplant was > 70% [9-11]. Older (> 55 years of age) patients or younger patients with medical co-morbidities that preclude full dose conditioning undergo reduced intensity conditioning (RIC) allogeneic HCT. The 2-year risk of disease relapse in patients with acute leukemia in CR who received RIC allogeneic HCT was > 50% [12, 13]. Similarly, disease relapse remains the major cause of treatment failure for patients with T-cell, large B-cell and Hodgkin lymphomas and chronic lymphocytic leukemia (CLL) and occurs in > 40% who undergo RIC allogeneic HCT with chemotherapy, sub-lethal total body irradiation (TBI), or total lymphoid irradiation combined with anti-thymocyte globulin (TLI/ATG) [13-18].

2.3 Treatment for Disease Relapse Following Allogeneic HCT

Disease relapse following allogeneic HCT remains an ominous clinical event, which usually results in progressive disease and death. Treatment strategies of patients with relapse following

allogeneic HCT can often be further complicated by the overall general poor clinical status of the patient. Strategies for the treatment of disease relapse in these patients include the cessation of post-transplantation immune suppression medication, salvage chemotherapy with or without irradiation, a second allogeneic HCT, or the infusion of donor leukocytes (DLI). Despite these interventions few patients beyond those with chronic myelogenous leukemia (CML) can be returned to durable remissions and the overall survival (OS) at 2 years following disease relapse was < 20% [19, 20]. Given that disease relapse is relatively common after transplant, and that few if any patients can be returned to durable remission once relapse has occurred, a desired goal would be to improve the transplant strategy and avoid the serious problem of post-transplant disease relapse.

2.4 Graft Versus Tumor Reactions

A major mechanism of cancer eradication following allogeneic HCT is the immunological-based recognition of residual host tumor cells by donor-derived immune cells contained in the donor graft. This phenomenon, termed graft-versus-tumor (GVT) reactions, is supported by various lines of evidence. The initial observations in support of GVT reactions stemmed from studies that used T-cell depleted (TCD) donor grafts whereby graft-versus-host disease (GVHD) was eliminated; however, without donor T-cells in the donor inoculum patients suffered a high incidence of disease recurrence [21]. The importance of GVT reactions was further demonstrated by improved disease control and fewer relapses following HLA identical sibling (allogeneic) transplantation compared to syngeneic (identical twin) transplantation for patients with hematologic malignancies [22]. The three year probability for relapse of leukemia was substantially higher following syngeneic compared to allogeneic HCT in acute myelogenous leukemia (AML) (52% vs 16%) and CML (40% vs 7%) following treatment using full dose transplant conditioning regimens [22]. The increased risk of relapse in syngeneic transplants counterbalanced the beneficial effect of the lack of GVHD. Perhaps the most compelling evidence comes from the observation that the infusion of donor leukocytes obtained from the original donor in patients who have disease relapse following allogeneic HCT resulted in a GVT effect (23).

2.5 Reduced Intensity Transplant Conditioning

Following the recognition that a main mechanism of disease control after allogeneic HCT is by donor derived immune mediated GVT reactions, multiple groups, including our own at Stanford, developed reduced intensity transplant conditioning (RIC) regimens that shifted the burden of disease control from high doses of chemoradiotherapy to the donor immune system [23-25]. The low intensity transplant conditioning has allowed older patients and those with medical co-morbidities to proceed with transplant whereas, before these patients were excluded from allogeneic transplantation as the full dose conditioning regimens were associated with prohibitive toxicities. As a consequence of the low-dose conditioning, host hematopoietic and immune cells persist and result in a state of mixed hematopoietic and lymphoid chimerism (MC) that may convert to full donor chimerism (FDC) over a variable time course (13, 28-30). Importantly, the achievement of early (before Day 60) FDC appears to be a necessary precondition for disease control ([26, 27]. We and others have reported that irrespective of the specific type of RIC regimen used, the relapse risk is significantly higher in patients with persistent MC compared to those with FDC, and likely reflects tolerance of donor cells to recipient tissues (13, 28-30). In a report detailing the outcomes of 111 allogeneic HCT recipients from HLA-matched and single

antigen mismatch donors following TLI-ATG conditioning for leukemia and lymphoma there was a very low incidence of severe (Grade 2 to4) acute GVHD (< 5%), and a low incidence of non-relapse related mortality at 1 year (< 5%) (13). Whereas almost all patients who failed to achieve FDC experienced disease relapse, the actuarial event free survival was more than 55% in the patients who achieved > 95% donor type chimerism, with observations extending up to 6 years (13).

2.6 Rationale to include very low-dose TBI in NMA TLI-ATG conditioning

Low-dose TBI (doses of 50, 100, 150 and 200 cGy) is well established to improve donor hematopoietic stem cell (HSC) engraftment due to targeting of marrow HSC niches.[28] Engraftment is dose-dependent with more robust engraftment at higher doses. Yet increasing the dose of TBI is balanced by the risk of aggravating GVHD as higher doses (> 150 cGy) of TBI which may increase GVHD development by promoting intestinal inflammation with subsequent release of DAMPS and PAMPS.[29] It is hypothesized that in the current protocol the addition of one very low-dose (80 cGy) of TBI as a substitute for the last dose of TLI will help promote donor HSC engraftment due to its ability to help clear marrow niche space yet avoid the widespread intestinal inflammation typically associated with higher doses of TBI. Improved donor cell engraftment is associated with reduced rates of post-transplant disease relapse and improving donor cell engraftment without increasing GVHD is a significant goal of transplantation.

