2.7 Study Rationale

The persistence of mixed hematopoietic cell chimerism is associated with a significantly high risk of disease relapse after allogeneic HCT [13, 28-30]. Once the patient's disease has relapsed after allogeneic HCT, the likelihood for long-term survival is poor. Therefore, a strategy that can help promote conversion of mixed to complete hematopoietic cell chimerism prior to disease relapse, and does not promote significant GVHD has the potential to help improve the outcomes of allograft recipients by reducing the risk of disease relapse. The goal of the current proposed trial will be to determine if the addition of very low-dose TBI to standard TLI-ATG conditioning therapy will increase the proportion of patients with FDC at Day 28 post-transplant, without reducing tolerability or increasing transplant morbidity. We **hypothesize** that the addition of very low-dose TBI at 80 cGy to TLI-ATG will result in at least a 30% increase in the proportion of patients with FDC in the CD3 subset at Day 28 post-HCT. This study will follow a single-arm Simon 2-stage trial principle. In Simon stage 1, we will enroll 11 patients, and if 5 or fewer patients respond, defined as $\geq 95\%$ donor chimerism in the CD3 compartment at Day 28, we will stop for futility. If 6 or more respond in Simon stage 1, then in stage 2 we will continue to enroll a full sample of 20 patients and declare success if a total of 11 or more patients respond. The primary endpoint will be the determination of the rate of conversion from mixed to complete donor chimerism. Secondary endpoints will include the risk of acute and chronic GVHD, freedom from disease progression, event-free and overall survival, and the relapse rate. The goal is to improve the rate of attaining complete chimerism without increasing the risk of GVHD. If following the Simon 2-stage trial the results are encouraging, we will expand our experience to a broader trial to determine if the TLI/ATG/low-dose TBI is associated with significantly lower rates of disease relapse.

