2.8 Study Design

This is a single institution open-labeled single treatment study evaluating the safety and efficacy of very low-dose TBI added to TLI-ATG conditioning in adults undergoing allogeneic HCT from related and unrelated donors. Enrollment of 20 patients is expected to be completed in less than 2 years. The study will involve a single non-randomized intervention arm of administering TBI 80 cGy on Day -1 of standard TLI ATG conditioning. The total duration of patient study participation is 12 months. Per regular medical care for HSC transplant patients, all recipients will be followed long term and tracked via the Stanford BMT patient database for overall survival; event-free survival; and late complications such as but not limited to relapse; late chronic GVHD; and infections.

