4.1 Study Treatment Schedule

Transplant Schedule (See also Section 7 Study Calendar)

Week 1

Monday Day -11	Tuesday Day -10	Wednesday Day -9	Thursday Day -8	Friday Day -7	Saturday Day -6	Sunday Day -5
TLI 120 cGy	TLI 120 cGy	TLI 120 cGy	TLI 120 cGy	TLI 120 cGy	Rest	Rest
ATG **** 1.5 mg/kg + solumedrol 1.0 mg/kg	ATG 1.5 mg/kg + solumedrol 1.0 mg/kg					

Week 2 and beyond

Monday Day -4	Tuesday Day -3	Wednesday Day -2	Thursday Day -1 *	Friday Day 0	Saturday Day +1	Day 28 +/- 5 days	Day 56 +/- 5 days	Day 90 +/- 5 days
TLI 120 cGy	TLI 120 cGy	TLI 120 cGy	TLI 120 cGy	Mobilized PBMC				
	Start Tac 0.05 mg/kg oral BID***		TBI 80 cGy	Start MMF **				
						PB STRs	PB STRs	PB STRs

* As a guideline 5 hour interval will be provided between TLI and TBI on Day -1. No lung blocks will be used for TBI. The dose rate will be \leq 2 Gy/minute. The Pre-HCT radiation oncology consultation will include simulation for both TLI and TBI and should be scheduled as such

** MMF 15 mg/kg PO BID for matched related donors; 15 mg/kg PO q8 hours for unrelated donors (URDs) or mismatched related donors. Physician discretion can round up or round down MMF to the nearest 250m/dose.

*** Tac starting dose is a recommended guideline yet based on Physician/APP discretion this start dose can be modified, typically lowered due to concern about drug-drug interaction and possible Tac toxicity.

**** ATG dosing is based on actual weight yet if >15 kg above ideal body weight the ordering MD has the discretion to dose ATG based on actual weight or dose based on adjusted weight, both are acceptable.

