4.3 Alternatives

Alternative therapies will be discussed with each patient and would potentially include allogeneic transplantation using TLI and ATG conditioning without TBI or allogeneic transplantation using

other transplant conditioning or other investigational therapies, or best of care non-transplantation therapy.

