7. STUDY CALENDAR

	Pre-enrollment requirements		Day -11, -10, -9, -8, -7	Day -4	Day -3	Day -2	Day -1	Day 0	Day 28 +/- 7 days	Day 56 +/- 14 days	Day 90 +/- 14 days	Day 180 +/- 4 weeks	Day 360 +/- 8 weeks
	Day -180 to -13	Day -42 to -12											
Informed consent	X												
Demographics	X												
Donor evaluation	X												
B-HCG ^a		X											
Height		X											
Weight		X						X	X	X	X		
Medical history	X							X	X	X	X		
Concurrent meds		X						X	X	X	X		
Physical exam	X							X	X	X	X		
Vital signs ^b		X						X	X	X	X		
Performance status	X							X	X	X	X		
Central venous catheter		X											
Blood sample for:		↓						↓	↓	↓	↓	↓	↓
CBC w/diff		X						X	X	X	X		
Serum chemistry ^c		X						X	X	X	X		
STR analysis ^d									X	X	X	X	X
TLI ^e			X	X	X	X	X						
TAC ^f					X								
ATG ^g			X										
TBI ^h							X						
PBSC Infusion								X					
MMF ⁱ								X					
SAE evaluation								X - Weekly from Day 0 through Day 90					
Disease Status Assessment ^j	X									X	X as indicated	X as indicated	

- a: Pregnancy test for women of childbearing potential only.
- b: Temperature, blood pressure, and pulse.
- c: Albumin, alkaline phosphatase, total bilirubin, calcium, chloride, creatinine, glucose, potassium, total protein, AST, ALT, sodium
- e: TLI: Total lymphoid irradiation, 120 cGy.
- f: TAC: Tacrolimus
- g: ATG: Anti thymocyte globulin, 1.5 mg/kg with solumedrol 1.0 mg/kg.
- h: TBI: Total body irradiation, 80 cGy.
- i: MMF: Mycophenolate mofetil, by mouth.
- j: Response assessment as per disease histology, and may include CT, PET, and/or MRI imaging, and bone marrow biopsy or aspiration (refer to Appendix B), and is typically performed around Day 90 post-transplant (Day 0).
- k: Short tandem repeat (STR) analysis (by comparison to subject's pre-study HLA analysis) on Day 28 +/- 7 days; Day 56 +/- 14 days; Day 90 +/- 14 days; Day 180 +/- 4 weeks; Day 360 +/- 4 weeks, and thereafter as per standard of care.

8. MEASUREMENTS and STATISTICAL METHODS

Our extensive experience with the TLI ATG conditioning for allogeneic HCT in cancer patients showed a 30 to 40% incidence of FDC at Day 90, with a 95% confidence interval of 10 to 49%. The non-relapse mortality (NRM) was 3% (95% CI: 0 to 14%) at 100 days and 6% (95% CI: 1 to 28%) at 1 year. The incidence of acute GVHD by Day 100 was 6% (0.7 to 22%).

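### Is the 80 cGy TBI added to standard TLI/ATG or given in place of the last TLI dose, and does the mixed wording affect the trial's conclusion?

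*Combined protocol and SAP*

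**What the plan says.** All references are to the combined protocol and SAP.

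**Substitution wording.** Section 2.6, which gives the rationale for TBI, hypothesises a benefit from the "addition of one very low-dose (80 cGy) of TBI as a substitute for the last dose of TLI".

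**Addition wording.** The synopsis speaks of "a single administration of low-dose TBI to standard TLI/ATG non-myeloablative transplant conditioning". Section 2.7 sets the trial's goal in terms of "the addition of very low-dose TBI to standard TLI-ATG conditioning therapy". Section 2.8 describes the single arm as "administering TBI 80 cGy on Day -1 of standard TLI ATG conditioning".

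**What is scheduled.** The table in Section 4.1 lists TLI 120 cGy on Days -11 to -7 and again on Days -4 to -1, with TBI 80 cGy on Day -1. Its footnote reads "As a guideline 5 hour interval will be provided between TLI and TBI on Day -1". The Section 7 calendar marks both TLI and TBI on Day -1.

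**The reference.** Section 4.3 lists, among the alternatives to be discussed with patients, "allogeneic transplantation using TLI and ATG conditioning without TBI", without a fraction count. Section 8 reports: "Our extensive experience with the TLI ATG conditioning for allogeneic HCT in cancer patients showed a 30 to 40% incidence of FDC" (at Day 90), again without a TLI dose or fraction count. Section 10.1 tests a null rate of 0.40 against 0.70 and names no source for the 0.40.

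**The concern.** There is no control group. A positive result means only that the Day 28 full-donor-chimerism rate exceeded a benchmark, and its interpretation rests on how the study regimen differs from the one behind that benchmark. If TBI was added to an unchanged TLI course, one component changed. If TBI replaced a TLI fraction, two components changed together, and a report crediting the added TBI alone would misdescribe the comparison. The same holds for the conclusion that GVHD was not increased.

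The two wordings cannot both be literally true of the same standard course, and no section states how many TLI fractions that course contains. Section 2.7 plans a broader trial if results are encouraging, so an unclear description could carry forward.

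**Working it through.** **Step 1. Is the study regimen itself in doubt?** Input: the Section 4.1 table and the Section 7 calendar.

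- TLI days: 5 (Days -11 to -7) + 4 (Days -4 to -1) = 9.
- TLI total: 9 × 120 = 1080 cGy. With TBI: 1080 + 80 = 1160 cGy.

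If the Section 2.6 clause were read as removing the listed Day -1 fraction, TLI would be 8 × 120 = 960 cGy. That conflicts with the table, with the calendar, and with the footnote on the interval between the two treatments that day. The operative sections agree on nine fractions, so staff following the schedule have one regimen to deliver.

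**Step 2. How does that regimen relate to standard TLI/ATG?** The standard count is not given, so both rows below are assumptions.

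| Assumed standard course | Standard TLI | Study TLI | Difference |
|---|---|---|---|
| 9 fractions (TBI purely added) | 9 × 120 = 1080 cGy | 1080 cGy | 0 cGy |
| 10 fractions (schedule already reflects a replacement) | 10 × 120 = 1200 cGy | 1080 cGy | 120 cGy; 120/1200 = 10% |

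Section 2.8 places TBI on Day -1 of standard conditioning, and Section 4.1 sets out that conditioning with TLI on Day -1. Read together, they present the nine-fraction course as the standard one, which is the first row. The second row needs a ten-fraction standard that appears nowhere in the documents. This is a reading of the text, not a judgement on which regimen is right.

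**Step 3. Does either reading alter the test?** Inputs: null rate 0.40 and alternative 0.70 (Section 10.1); 11 patients in stage 1, stop at 5 or fewer responders, 20 in total, success at 11 or more (Section 2.7). Stage 2 adds 9 patients.

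P(success | p) = Σ over x = 6 to 11 of C(11, x) pˣ (1 − p)¹¹⁻ˣ × P[Bin(9, p) ≥ 11 − x]

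- At p = 0.40: 0.0990, against the stated type I error of 0.10.
- At p = 0.70: 0.9020, against the stated power of 0.90.

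The plan's figures are reproduced. The formula contains only the boundaries and the response rate, and no term depends on how TBI relates to TLI. (Section 10.1 prints a stage 1 boundary of 7, which gives 0.023 and 0.568. That is a separate discrepancy and does not bear on this point.)

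**Step 4. Does either reading alter the result?** The primary endpoint is the proportion with at least 95% donor CD3 cells at Day 28. Patients treated, assay, count of responders and decision are identical under both wordings. Only the sentence describing the contrast with past practice could differ.

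**The case for a change.** The strongest case for acting runs as follows. Section 2.6 is current text, refers expressly to this protocol, and is the only place that relates TBI to the TLI course fraction by fraction. The schedule settles what is given here but not what was given in the historical experience. With no concurrent control, an accurate account of the contrast is most of what the reader has. Enrolment is closed (Section 6), but the analysis and the public posting of outcomes are still to come, so the wording can still be put right.

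Much of this stands. The contradiction is on the page, and the reference TLI course should be stated when results are reported.

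What does not stand is that the plan is left open in a way that could change what is done or found. The only non-zero difference, 120 cGy, comes from assuming that the Section 2.6 clause is literally right and that the schedule already reflects it. The link between the 0.40 and any particular TLI course is itself an inference. Section 4.3 is a short list of options for discussion with patients, so its silence on fraction count shows little. Attribution is limited in any case by the lack of a control group and by a benchmark observed at Day 90, with a 95% interval of 10 to 49%, against an endpoint at Day 28. Tidying the clause would not remove those limits. Finally, the documents contain nothing from which an effect of one TLI fraction on chimerism could be computed.

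**Conclusion.** The concern does not call for a change to the plan. It combines a clerical inconsistency in a background section with a missing detail, the TLI course of the historical reference, which the analysts would supply when describing the comparison. Section 2.6 should be reconciled with the synopsis and Sections 2.7, 2.8, 4.1 and 7 so that all describe TBI in the same way. Which description is correct is for the investigators to say.

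The size is as follows. The scheduled regimen is 1080 cGy TLI plus 80 cGy TBI on any reading consistent with Sections 4.1 and 7. The change in type I error, power, sample size, boundaries and analysis is zero. The difference in TLI from standard is 0 cGy if the standard course has nine fractions, and 120 cGy (10%) if it has ten.

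This rests on two assumptions: that patients were treated according to the schedule and calendar, and that the final report will say what the reference TLI/ATG course was. If the historical course did differ by a fraction, the report should describe both changes, but the trial's test and its numerical result would be the same.
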